7.2.4 Laboratory values

7.2.4.1 Serum creatinine

Serum creatinine will be categorized in two categories (7):

- Normal levels: 0.6-1.2 mg/dl in males and 0.5-1.1 mg/dl in females
- High/low levels

7.2.4.2 Creatinine clearance

Creatinine clearance will be estimated using Cockcroft-Gault formula (7):

$$CCr = (140 - \text{Age}(\text{years})) \times \text{Weight} (\text{kg}) \times [0.85 \text{ if female}] / 72 \times [\text{Serum Creatinine} (\text{mg/dL})]$$

Chronic Kidney Disease will be categorized according to these values, included in Clinical Practice Guidelines for Chronic Kidney Disease: Evaluation, Classification, and Stratification:

- ≥ 90 : Kidney damage with normal or increased glomerular filtration rate (GFR)
- 60-89: Kidney damage with mild decreased GFR
- 30-59: Moderate decrease in GFR
- 15-29: Severe decrease in GFR
- < 15 : Kidney failure

7.2.4.3 ALT, AST and bilirubin values

ALT, AST and bilirubin will be categorized in two categories, according to [REDACTED] ([https://www.\[REDACTED\].org/tests-procedures/liver-function-tests/about/pac-20394595](https://www.[REDACTED].org/tests-procedures/liver-function-tests/about/pac-20394595)):

ALT (GPT):

- Normal values: 7-55 UI/L
- High/low values

AST (GOT):

Document:	H:\HOR-Europe\2019\2512352 - Study on anticoagulation management - BI\Proyecto\Estadística\SAP\S AP_REBELD_version1.0_08072020.docx		
Author:	[REDACTED]	Version Number:	Version 1.0
		Version Date:	[08072020]

Template No.: RWI_TP_BIOS0013 Revision 1

Reference: RWI_WI_BIOS0015

Effective Date: 15Jun2018

- Normal values: 8-48 UI/L
- High/low values

Bilirubin:

- Normal values: 0.2-1.2 mg/dl
- High/low values

7.2.4.4 *Haemoglobin and platelets*

Haemoglobin and platelets levels will be categorized in two categories, according to American cancer society (<https://www.cancer.org/content/dam/CRC/PDF/Public/7174.pdf>):

Haemoglobin:

- Normal values: 12-18 g/dL
- High/low values

Platelets:

- Normal values: 150-450 x103/ μ L
- High/low values

7.2.5 **Time since NVAF diagnosis**

The number of years since diagnosis will be obtained from number of years between date of NVAF diagnosis and date of study visit as follows:

$$\text{Time of NVAF evolution (years)} = (\text{date of study visit} - \text{date of NVAF diagnosis} + 1) / (365.25).$$

7.2.6 **Duration of VKA treatment**

VKA treatment duration in years will be calculated as number of months/12 (in case of months specified). In case of more than one VKA treatment, the total VKA treatment duration will be calculated as the sum of the years in treatment of each one.

Document:	H:\HOR-Europe\2019\2512352 - Study on anticoagulation management - BI\Proyecto\Estadistica\SAP\S		
	AP_REBELD_version1.0_08072020.docx		
Author:	██████████	Version Number:	Version 1.0
		Version Date:	[08072020]

Template No.: RWI_TP_BIOS0013 Revision 1

Reference: RWI_WI_BIOS0015

Effective Date: 15Jun2018

7.2.7 Duration since the first NOAC

The number of months since the first NOAC initiation date until the study visit date will be obtained as follows:

Duration since the first NOAC (months) = (date of study visit – date of first NOAC + 1)/(30.5).

Duration since the first NOAC initiation until study visit will be categorized as >4 months and ≤4 months.

7.2.8 Duration since NVAF diagnosis until first NOAC initiation

The number of months since the NVAF diagnosis date until the first NOAC initiation date will be obtained as follows:

Duration since the NVAF diagnosis until first NOAC initiation (months) = (date of first NOAC – date of NVAF diagnosis + 1)/(30.5).

7.2.9 Duration of first NOAC treatment

The duration of the first NOAC treatment will be calculated as the number of years (or months, depending on the data) between stop date and start date for the NOAC treatment with the minimum start date:

Duration of the first NOAC (years) = (stop date of first NOAC – start date of first NOAC + 1)/(365.25)

or

Duration of the first NOAC (months) = (stop date of first NOAC – start date of first NOAC + 1)/(30.5)

In the case the first NOAC has not been finished, the study visit date will be considered as the stop date (censored cases).

Document:	H:\HOR-Europe\2019\2512352 - Study on anticoagulation management - BI\Proyecto\Estadistica\SAP\S		
	AP_REBELD_version1.0_08072020.docx		
Author:	██████████	Version Number:	Version 1.0
		Version Date:	[08072020]

Template No.: RWI_TP_BIOS0013 Revision 1

Reference: RWI_WI_BIOS0015

Effective Date: 15Jun2018

7.2.10 Duration of new NOAC treatments

The duration of new NOAC treatment will be calculated as the number of years (or months, depending on the data) between stop date and start date for the new NOAC treatment:

$$\text{Duration of the new NOAC (years)} = (\text{stop date of new NOAC} - \text{start date of new NOAC} + 1) / (365.25).$$

or

$$\text{Duration of the new NOAC (months)} = (\text{stop date of new NOAC} - \text{start date of new NOAC} + 1) / (30.5).$$

In the case the new NOAC has not been finished, the study visit date will be considered as the stop date.

7.2.11 Total time in NOAC treatment

NOAC treatment duration in years will be calculated as the sum of the years of each NOAC treatment. The duration of the each NOAC treatment will be calculated as:

$$\text{Duration of each NOAC (years)} = (\text{stop date of NOAC} - \text{start date of NOAC} + 1) / (365.25).$$

For the last NOAC treatment (receiving at study visit) the stop date will be the study visit date.

In other hand, in the case there are periods of interruption of the NOAC treatment, only the time that they have been in treatment will be considered. In this case, the time in each period will be calculated from the previous formula, adding the different periods in treatment.

7.2.12 Number of switches

The number of switches will be defined as the number of changes to another NOAC.

Document:	H:\HOR-Europe\2019\2512352 - Study on anticoagulation management - BI\Proyecto\Estadistica\SAP\S		
	AP_REBELD_version1.0_08072020.docx		
Author:	██████████	Version Number:	Version 1.0
		Version Date:	[08072020]

Template No.: RWI_TP_BIOS0013 Revision 1

Reference: RWI_WI_BIOS0015

Effective Date: 15Jun2018

7.2.13 Total time in treatment with antiplatelet agents

Time in treatment with antiplatelet agents (in years or months) will be calculated as the sum of the years of each antiplatelet treatment. The duration of each antiplatelet treatment will be calculated as:

Duration of the each antiplatelet (years) = (stop date of antiplatelet – start date of antiplatelet + 1)/(365.25).

or

Duration of the each antiplatelet (months) = (stop date of antiplatelet – start date of antiplatelet + 1)/(30.5).

For the last antiplatelet treatment (if it is received at study visit) the stop date will be the study visit date.

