8. RESEARCH QUESTION AND OBJECTIVES

This study has been designed in order to describe the current non-vitamin K antagonist oral anticoagulants (NOACs) management in elderly patients in Spain.

Primary objective: To describe the pattern of usage of NOACs prescribed according to their Summary of Product Characteristics (SmPC), by current NOAC type and dose, in elderly patients (≥ 75 years-old) with non-valvular atrial fibrillation (NVAF) at the time of the study visit.

Secondary objectives:

1. To describe patients characteristics at the time of the study visit by current NOAC type stratified by duration since first NOAC initiation.
2. To describe OAC treatment management since first NOAC initiation until the study visit by duration since first NOAC initiation: previous vitamin K antagonists (VKA) treatment, first NOAC treatment duration, dose changes, switch between NOACs and reasons for switch, total NOAC treatment duration and additional antiplatelet treatment.
3. To describe the Clinical Frailty Scale grading, CFS ([19](#)), at the time of the study visit, by current NOAC type.
4. To describe first NOAC usage by NOAC type, for primary prevention or secondary prevention, at the time of first NOAC initiation.

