3.2 Secondary Objectives

The secondary objectives are:

1. To describe patients' characteristics at the time of the study visit by current NOAC type stratified by duration since first NOAC initiation.
2. To describe OAC treatment management since first NOAC initiation until the study visit by duration since first NOAC initiation: previous vitamin K antagonists (VKA) treatment, first NOAC treatment duration, dose changes, switch between NOACs and

Document:	H:\HOR-Europe\2019\2512352 - Study on anticoagulation management - BI\Proyecto\Estadistica\SAP\SAP_REBELD_version1.0_08072020.docx		
Author:	██████████	Version Number:	Version 1.0
		Version Date:	[08072020]

Template No.: RWI_TP_BIOS0013 Revision 1

Reference: RWI_WI_BIOS0015

Effective Date: 15Jun2018

reasons for switch, total NOAC treatment duration and additional antiplatelet treatment.

3. To describe the Clinical Frailty Scale grading, CFS (1), at the time of the study visit, by current NOAC type.
4. To describe first NOAC usage by NOAC type, for primary prevention or secondary prevention, at the time of first NOAC initiation.

Further objective: To evaluate the appropriateness of prescribed therapy based on Spanish health authorities' recommendations (2) (therapeutic positioning report) and other regional guidelines by NOAC type (if there are enough patients for a NOAC type), at the time of first NOAC initiation.

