14.2.2 OAC treatment management

OAC treatment management (since first NOAC initiation until the study visit date), based on the following variables:

- Previous vitamin K antagonist (VKA) treatment (yes/no), VKA treatment duration in years
- Duration since NVAF diagnosis until first NOAC initiation,
- Duration of first NOAC treatment (first NOAC active substance, start and stop date, first NOAC dose and its dose changes),
- Switch to new NOAC (active substance, start/stop date, dose and dose changes, reason for switch to new NOAC): number of patients that switch their first or further NOAC and mean number of switches.
- Total time in NOAC treatment
- History and current antiplatelet treatment (yes/no, start date, end date, active substance).

Patients will be also stratified by the duration since the first NOAC initiation date until the study visit date (> 4 months / ≤ 4 months).

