*Only patients who stopped second NOAC treatment

Table 39. will be repeated for each treatment switch during follow-up.

Document: H:\HOR-Europe\2019\2512352 - Study on anticoagulation management - BI\Proyecto\Estadística\SAP\S
AP_REBELD_version1.0_08072020.docx

Author: [REDACTED]

Version Number:

Version 1.0

Version Date:

[08072020]

Template No.: RWI_TP_BIOS0013 Revision 1

Reference: RWI_WI_BIOS0015

Effective Date: 15Jun2018

Table 40. Total time (in years) in NOAC treatment

		≤4 months	>4 months	Total
Total time in NOAC treatment (in years)	Valid N Mean (SD) Median (Q1-Q3) Min-Max N missing			
Total time in NOAC treatment (cat)	Valid N <1 year 1-2 years 2-3 years >3 years N missing			

Table 41. History and current antiplatelet treatment according to duration since the first NOAC initiation

		≤4 months	>4 months	Total
Antiplatelet treatments received (all)	Valid N Aspirin Clopidogrel Prasugrel Ticlopidine Ticagrelor Cilostazol Triflusal Dipyridamole Others N missing			
Time in treatment with antiplatelet agents (in years)	Valid N Mean (SD) Median (Q1-Q3) Min-Max N missing			
Current antiplatelet treatment (at study visit)	Valid N None			

Document: H:\HOR-Europe\2019\2512352 - Study on anticoagulation management - BI\Proyecto\Estadistica\SAP\S AP_REBELD_version1.0_08072020.docx

Author: [REDACTED] Version Number: Version 1.0
Version Date: [08072020]

Template No.: RWI_TP_BIOS0013 Revision 1

Reference: RWI_WI_BIOS0015

Effective Date: 15Jun2018

		≤4 months	>4 months	Total
	Aspirin			
	Clopidogrel			
	Prasugrel			
	Ticlopidine			
	Ticagrelor			
	Cilostazol			
	Triflusal			
	Dipyridamole			
	Others			
	N missing			

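### Time on antiplatelet agents is summed drug by drug, so overlapping courses count twice, and Table 41 does not separate years before the first NOAC from time since it

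*SAP*

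**What the plan says.** SAP 7.2.13 defines the total as follows: it "will be calculated as the sum of the years of each antiplatelet treatment". Each drug contributes its own stop date minus its own start date plus one day, divided by 365.25 for years or 30.5 for months. On ongoing treatment the section says: "For the last antiplatelet treatment (if it is received at study visit) the stop date will be the study visit date". It contains no rule for two agents taken at once and no lower date limit, and no other section of the SAP or protocol supplies either.

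The data are listed within outcome 2 in SAP 14.2.2 (and identically in Protocol 9.3.2.2): "History and current antiplatelet treatment (yes/no, start date, end date, active substance". That outcome is introduced as "OAC treatment management (since first NOAC initiation until the study visit date), based on the following variables". The objective in Protocol 8 reads "To describe OAC treatment management since first NOAC initiation until the study visit by duration since first NOAC initiation", and its list of components, as given in SAP 3.2, ends with "total NOAC treatment duration and additional antiplatelet treatment".

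The total is reported in Table 41 (SAP 17.3.2, by ≤4 or >4 months since first NOAC). It is repeated in Table 45 (SAP 17.4, by current NOAC type). Both tables also have a row for all antiplatelet agents ever received and a row for current agents.

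**The concern.** A sum of durations equals time in treatment only if the courses follow one another. For NOACs that is a fair assumption: SAP 7.2.11 and 7.2.12 treat them as successive treatments with switches, and 7.2.11 deals with interruptions. The antiplatelet rule copies the sum without anything that makes it safe. Tables 41 and 45 list aspirin and the other agents as separate entries, so a patient on two at once contributes two durations for the same calendar days.

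The second problem is the time base. The row sits under an outcome headed as covering first NOAC to study visit and serving an objective about antiplatelet treatment given in addition. Yet a course that ended before the first NOAC counts in full, and a course that spans the first NOAC is not divided. A reader of Table 41 could take years of earlier treatment for treatment given alongside the NOAC, most visibly in the ≤4-month column.

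**Working it through.** The plan states no figure for this variable, so there is none to reproduce. The check applies the 7.2.13 formula to constructed histories.

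**Inputs.** From SAP 7.2.13: total = Σ(stop − start + 1)/365.25. From SAP 7.2.7: months since first NOAC = (visit − first NOAC + 1)/30.5, cut at 4 months. Assumed here: a visit on 15 January 2020 and the treatment dates below.

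**Compared with:** distinct calendar days on at least one agent, divided by 365.25; and the same count restricted to days on or after first NOAC.

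| Assumed history | SAP sum | Calendar time | Since first NOAC |
|---|---|---|---|
| A. Two agents over the same 365 days after first NOAC, both stopped | (365 + 365)/365.25 = 2.00 | 365/365.25 = 1.00 | 1.00 |
| B. One agent for 10 years (3,652 days), stopped the day before first NOAC, itself 3.54 months before the visit | 3,652/365.25 = 10.00 | 10.00 | 0.00 |
| C. One agent for 10 years up to the visit, a second for 365 days within that span; first NOAC 2 years (730 days) before the visit | (3,652 + 365)/365.25 = 11.00 | 3,652/365.25 = 10.00 | 730/365.25 = 2.00 |
| D. Two agents in sequence, no overlap, all after first NOAC (350 + 380 days) | 730/365.25 = 2.00 | 2.00 | 2.00 |

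A isolates the overlap error, B isolates the time base, and C shows both together. D shows that the formula is right when agents are sequential and start after the first NOAC, so the discrepancy comes only from those two sources.

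**Ceiling in the ≤4-month column.** Four months is 4 × 30.5 = 122 days, and 122/365.25 = 0.33 years. Any larger value in that column must contain time before the first NOAC or double counting.

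**Two agents both ongoing at the visit.** Only one is given a stop date. Suppose one agent has run for 10 years and a second for 1 year, both continuing. Calendar time is 10.00 years. If the programmer uses the visit date for both, the total is 10.00 + 1.00 = 11.00. If it is used only for the most recently started agent and the other is dropped as incomplete, the total is 1.00. The text does not settle which.

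**The case against.** The best defence concerns the time base. Outcome 2 lists antiplatelet history explicitly, next to other items that precede the first NOAC: previous VKA use, VKA duration, and time from NVAF diagnosis to first NOAC. Table 41 is titled as history and current treatment, and its row label, "Time in treatment with antiplatelet agents (in years", claims no window. A total over recorded history is therefore a legitimate reading and need not be removed. That stands. What remains is that the VKA and diagnosis items show from their labels that they lie before the NOAC, whereas this row mixes the two periods and gives no way to separate them.

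A reader might go further and infer four things that the documents do not support.

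- *That the objective requires time on antiplatelet and NOAC together.* It asks only for additional antiplatelet treatment, and the protocol abstract states that no specific safety outcome is defined. Cutting at first NOAC would not give combined exposure anyway, because SAP 7.2.11 allows for NOAC interruptions.
- *That Table 45 must also be cut at first NOAC.* It is an additional table (SAP 17.4), listed as new in 4.6 and as exploratory in 14.6, so the outcome 2 window does not govern it.
- *That the error biases comparisons between NOACs, or falls mainly on patients with coronary disease.* This may be plausible, but no figure in either document bears on it.
- *That all dual therapy is doubled.* Completed overlaps are. Two ongoing agents are undefined.

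It is also fair to say that the row is purely descriptive and that the ≤4-month split is made only if each group has at least 50 patients (SAP 14.3.2). Neither point affects the overlap error, which is wrong under any reading of time in treatment.

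**Conclusion.** The overlap error is certain from the stated rule: completed concurrent courses are counted once per drug, which is +100% for two agents with identical dates. The stop date for a second ongoing agent is missing from the text. Both affect the row in Tables 41 and 45. The lack of a split at first NOAC affects Table 41 only and is a matter of presentation: the historical total may stay, but it does not by itself describe the period that the outcome names.

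The examples are single constructed patients, not expected shifts in a reported mean or median. How far those shift depends on the frequency of overlapping and pre-NOAC antiplatelet use, which the documents do not give. The reading that all history is included rests on the wording of the outcome and of the table. The eCRF is not among the documents. If it records only agents taken since first NOAC, the split matters less, though an agent started earlier and continued would still carry its earlier years. The primary outcome and the NOAC durations are unaffected.

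**What to change.** Rewrite SAP 7.2.13 so that:

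1. time in treatment is the number of distinct calendar days on at least one antiplatelet agent, obtained by merging overlapping intervals within each patient, converted to years or months as now;
2. the study visit date is the stop date for every agent ongoing at the visit.

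In Table 41, keep the total, label it as recorded history, and add a separate row for the part from first NOAC start to the visit. Table 45 needs only the changes in 7.2.13.

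The cost is a few lines of text and slightly more programming. Start and end dates are already collected, so no new data are needed. Reported times will be shorter wherever completed courses overlap. The new row will have little spread in the ≤4-month column, where it cannot exceed 0.33 years, which is why the historical total should stay beside it.

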7.2.14 Clinical Frailty Scale (CFS)

The CFS score will be categorized in two categories, according to this ranges:

- 1) Frailty patients - CFS scoring >4
- 2) Non-frailty patients - CFS scoring ≤4

7.2.15 CHA2DS2-VASc Scale

The CHA2DS2-VASc total score will be categorized in three categories, according to the risk of stroke (8):

- 1) Low risk (score 0 in male; score 1 in female)
- 2) Moderate risk (score 1 in male; score 2 in female)
- 3) High risk (score ≥2 in male; score ≥3 in female)

Note: In the last update of European Society of Cardiology (ESC) guidelines 2016 the “female gender” is no longer considered by itself as an increase of the risk.

Document:	H:\HOR-Europe\2019\2512352 - Study on anticoagulation management - BI\Proyecto\Estadistica\SAP\S		
	AP_REBELD_version1.0_08072020.docx		
Author:	██████████	Version Number:	Version 1.0
		Version Date:	[08072020]

Template No.: RWI_TP_BIOS0013 Revision 1

Reference: RWI_WI_BIOS0015

Effective Date: 15Jun2018

7.2.16 HAS-BLED Scale

The HAS-BLED total score will be categorized in three categories, according to the bleeding risk (9):

- 1) Low risk (score 0)
- 2) Intermediate risk (score 1-2)
- 3) High risk (score ≥ 3)

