1. ABBREVIATIONS

ACE	Angiotensin Converting Enzyme inhibitors
ADR	Adverse Drug Reaction
AF	Atrial Fibrillation
AIDs	Acquired immune deficiency syndrome
ALT	Alanine Aminotransferase
ARB	Angiotensin-Receptor Blockers
AST	Aspartate Aminotransferase
BI	Boehringer Ingelheim
BID	Twice a day
BMI	Body Mass Index
CABG	Coronary Artery Bypass Grafting
CCI	Charlson Comorbidity Index
CFS	Clinical Frailty Scale
CHA2DS2-VASc	Congestive heart failure, Hypertension, Age (> 75), Diabetes mellitus, Stroke/TIA, Vascular disease, Age 65-74, Sex Category
CI	Confidence Interval
CKD	Chronic Kidney Disease
CRF	Case Report Form
eCRF	Electronic Case Report Form
EHRA	European Heart Rhythm Association
GFR	Glomerular Filtration Rate
HAS-BLED	Hypertension, Abnormal renal and liver function, Stroke (1 point), Bleeding history or predisposition, Labile INR, Elderly (>65 years), Drugs and Alcohol.
ICH	Intracranial haemorrhage
ICH-GCP	Harmonized Tripartite Guideline for Good Clinical Practice
INR	International Normalized Ratio
LVEF	Left ventricular ejection fraction
NSAIDs	Nonsteroidal Anti-Inflammatory Drugs
NYHA	New York Heart Association
NOAC	Non-vitamin K antagonist oral anticoagulant
NVAF	Non-valvular atrial fibrillation
OAC	Oral anticoagulant
PCI	Percutaneous coronary intervention

Document: H:\HOR-Europe\2019\2512352 - Study on anticoagulation management - BI\Proyecto\Estadistica\SAP\S AP_REBELD_version1.0_08072020.docx

Author: [REDACTED] Version Number: Version 1.0
Version Date: [08072020]

Template No.: RWI_TP_BIOS0013 Revision 1

Reference: RWI_WI_BIOS0015

Effective Date: 15Jun2018

PT	Preferred Terms
QD	Once a day
SADR	Serious Adverse Drug Reaction
SAHS	Sleep apnoea-hypopnoea syndrome
SAP	Statistical Analysis Plan
SmPC	Summary of Product Characteristics
SOC	System Organ Classes
SOPs	Standard Operating Procedures
TIA	Transitory ischemic attack
TLF	Tables/Listings/Figures
VKA	Vitamin K Antagonist

Document: H:\HOR-Europe\2019\2512352 - Study on anticoagulation management - BI\Proyecto\Estadistica\SAP\SAP_REBELD_version1.0_08072020.docx

Author: [Redacted]

Version Number: Version 1.0

Version Date: [08072020]

Template No.: RWI_TP_BIOS0013 Revision 1

Reference: RWI_WI_BIOS0015

Effective Date: 15Jun2018

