6.2 Full Analysis Set [FAS]

The full analysis set (FAS) will contain all enrolled subjects who provide informed consent for this study (ENR set) and fulfill all selection criteria. This is called “eligible patients” in the protocol.

Patients will be included in FAS if all of the following criteria are met:

1. Patients are willing and provide written informed consent prior to participate in this study
2. Patients \geq 75 years-old at the time of the study visit.
3. Patients with a diagnosis of non-valvular atrial fibrillation (NVAf).

Document:	H:\HOR-Europe\2019\2512352 - Study on anticoagulation management - BI\Proyecto\Estadistica\SAP\SAP_REBELD_version1.0_08072020.docx		
Author:	[REDACTED]	Version Number:	Version 1.0
		Version Date:	[08072020]

Template No.: RWI_TP_BIOS0013 Revision 1

Reference: RWI_WI_BIOS0015

Effective Date: 15Jun2018

4. Patients who are being treated with NOAC treatment according to the indication approved in the SmPC.
5. Patients who have started the NOAC treatment at least 3 months prior to the study visit.

Patients will be excluded from participating in this study, and will be excluded from this analysis set, if the following criterion is met:

1. Current participation in any clinical trial of a drug or device.
2. Patients who have any contraindication for NOAC treatment, according to the SmPC.

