14.6 Exploratory analysis

History and current antiplatelet treatment will be described by current NOAC type.

Treatment received at the time of thromboembolic and bleeding events will be described, including NOAC, VKA and antiplatelet treatments.

Doses of current NOAC treatment received by the patient will be described according to HAS-BLED score (as low, intermediate and high risk).

The percentage of underdosed and overdosed patients for current NOAC treatment will be described.

HAS-BLED total score (as <3 , $3-5$, ≥ 5) will be described according to NOAC and antiplatelet current treatment.

Multivariate logistic regression will be used to evaluate the association between the Clinical Frailty Scale (dependent variable: Frailty patients - CFS scoring >4 vs Non-frailty patients - CFS scoring ≤ 4) and the thromboembolic and the bleeding events (independent variables). To calculate this analysis, only events that have occurred subsequent to the start of anticoagulant therapy (not those prior to the start of VKA / NOACs) will be considered. Other factors will be age, sex, BMI, smoking habit, alcohol consumption, time since NVAf diagnosis, NVAf type, modified EHRA scale, procedures and interventions, comorbidity Charlson index and clinical risk factors. Univariate analysis will be performed. All variables which have a P value of less than 0.1 will be included in the multivariate analysis.

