NOAC	Valid N* No				

Document: H:\HOR-Europe\2019\2512352 - Study on anticoagulation management - BI\Proyecto\Estadística\SAP\SAP_REBELD_version1.0_08072020.docx

Author: [REDACTED] Version Number: Version 1.0
Version Date: [08072020]

Template No.: RWI_TP_BIOS0013 Revision 1

Reference: RWI_WI_BIOS0015

Effective Date: 15Jun2018

		Nasal	Pulmonary	Articular-muscular	Conjunctival
	Yes N missing				
Type of NOAC	Valid N Dabigatran Rivaroxaban Apixaban Edoxaban N missing				
Antiplatelet	Valid N* No Yes N missing				
Type of antiplatelet	Valid N Aspirin Clopidogrel Prasugrel Ticlopidine Ticagrelor Cilostazol Triflusal Dipyridamole Others N missing				

*Number of events in each column

One event could be associated with more than one treatment

Table 50. Current NOAC dose according to HAS-BLED

		HAS-BLED			
		Low risk	Intermediate risk	High risk	Total
Dabigatran dose	Valid N 110mg BID 150mg BID N missing				
Rivaroxaban dose	Valid N				

Document: H:\HOR-Europe\2019\2512352 - Study on anticoagulation management - BI\Proyecto\Estadística\SAP\SAP_REBELD_version1.0_08072020.docx

Author: [REDACTED] Version Number: Version 1.0
Version Date: [08072020]

Template No.: RWI_TP_BIOS0013 Revision 1

Reference: RWI_WI_BIOS0015

Effective Date: 15Jun2018

		HAS-BLED			
		Low risk	Intermediate risk	High risk	Total
	15mg QD 20mg QD N missing				
Apixaban dose	Valid N 2.5mg BID 5mg BID N missing				
Edoxaban dose	Valid N 30mg QD 60mg QD N missing				

Table 51. Overdosing and underdosing of current NOACs

		Appropriately dosed (n,%)	Underdosed (n,%)	Overdosed (n,%)
Dabigatran	Dabigatran (Age <80 years)			NA
	Dabigatran (Age ≥80 years)		NA	
	Dabigatran (75-79 years and HAS-BLED < 3)			NA
	Dabigatran (75-79 years and HAS-BLED ≥ 3)		NA	
	Dabigatran (creatinine clearance >50mL/min)			NA
	Dabigatran (creatinine clearance 30-50mL/min)			NA
Rivaroxaban	Rivaroxaban (creatinine clearance >50mL/min)			NA

Document: H:\HOR-Europe\2019\2512352 - Study on anticoagulation management - BI\Proyecto\Estadística\SAP\S AP_REBELD_version1.0_08072020.docx

Author: [REDACTED] Version Number: Version 1.0
Version Date: [08072020]

Template No.: RWI_TP_BIOS0013 Revision 1

Reference: RWI_WI_BIOS0015

Effective Date: 15Jun2018

		Appropriately dosed (n,%)	Underdosed (n,%)	Overdosed (n,%)
	Rivaroxaban (creatinine clearance ≤ 50 mL/min)		NA	
Apixaban	Apixaban (Age < 80 years)			NA
	Apixaban (Age ≥ 80 years)		NA	
	Apixaban (Body weight > 60 kg)			NA
	Apixaban (Body weight ≤ 60 kg)		NA	

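### The HAS-BLED low-risk class (score 0) cannot occur at age 75 or over, so the three-level description of NOAC dose by bleeding risk has only two usable levels

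*SAP*

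**What the plan says.** SAP 7.2.16 defines three HAS-BLED classes: "Low risk (score 0", then "Intermediate risk (score 1-2", then high risk at 3 or more. The SAP abbreviation list spells out the score, ending with "Labile INR, Elderly (>65 years), Drugs and Alcohol"; the protocol's list has the same age item. SAP 6.2 limits the Full Analysis Set to patients who are at least "75 years-old at the time of the study visit", matching the protocol's inclusion criterion.

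The three classes appear as rows in Tables 15 and 25. They are also the columns of an exploratory analysis added after the protocol (SAP 4.6): SAP 14.6 describes current NOAC dose by HAS-BLED "as low, intermediate and high risk", and the shell is "Table 50. Current NOAC dose according to HAS-BLED", with low, intermediate, high and total columns.

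Two other HAS-BLED groupings appear in the SAP. Section 7.2.17 uses a cut at ≥3 in its dabigatran dose classification for ages 75-79, and Table 51 shows it. Section 14.6 and Table 52 use <3, 3-5 and ≥5.

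The investigator assesses the total and enters it directly (SAP 7). SAP Table 3 lists only the total score, and protocol 9.10.2.1 exempts it from the rule that eCRF data derive from source documents.

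**The concern.** The classes in 7.2.16 suit a population in which some patients are 65 or younger. This study has none. If the bottom class is impossible by eligibility, three consequences follow.

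- Table 50 offers a three-step gradient of bleeding risk but can show only one contrast. The least-risk group that exists, patients whose only point is age, is merged with score 2 and called intermediate.
- A reader may take an empty low column as a finding about prescribing in this cohort, when it follows from the age criterion.
- A total of 0 entered in error would be reported as a low-risk patient. It would also suggest that the age item had been left out. If the same omission were made at a true score of 3, the recorded score would be 2. At age 75-79 that crosses the cut used in 7.2.17 and could change a dabigatran patient's dose category.

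**Working it through.** The plan states no figure on this point, so there is nothing to reproduce. The check sets the definitions side by side and enumerates the possible scores.

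**Inputs**
- Age item: over 65 years (SAP 1, Abbreviations).
- Eligible age: 75 or over (SAP 6.2).
- Classes: 0; 1-2; ≥3 (SAP 7.2.16).
- Assumption: one point per item. The documents give a point value only for stroke. Any positive weight for age leads to the same conclusion about the low class.

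**Step 1: minimum score.** Score = E + (sum of the other items), where E is the age item. Age ≥75 implies age >65, so E = 1. The other items sum to at least 0. Minimum = 1 + 0 = 1.

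**Step 2: which classes can be filled.** Fix E = 1 and let every other item be 0 or 1. Counting renal, liver, drugs and alcohol separately leaves 8 free items; counting one point per letter leaves 6.

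| Class | 8 free items (2^8 = 256 patterns) | 6 free items (2^6 = 64 patterns) |
|---|---|---|
| Low (0) | 0 | 0 |
| Intermediate (1-2) | 1 + 8 = 9 | 1 + 6 = 7 |
| High (≥3) | 256 − 9 = 247 | 64 − 7 = 57 |
| Attainable range | 1 to 9 | 1 to 7 |

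These are counts of item patterns, not expected shares of patients. They show only that the low class is unreachable under either way of counting.

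**Step 3: effect on the tables.** The low rows of Tables 15 and 25 and the low column of Table 50 must hold 0 valid patients. Table 50 reduces to 1-2 against ≥3.

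**Step 4: price of finer bands.** For illustration, take 500 patients spread evenly over four NOACs and over the bands, before the split by dose:
- two bands: 500 / (4 × 2) = 62.5 per cell
- three bands (1, 2, ≥3): 500 / (4 × 3) = 41.7
- four bands (1, 2, 3, ≥4): 500 / (4 × 4) = 31.3

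Real cells will be uneven, and some will be smaller.

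**Step 5: the other grouping.** In <3, 3-5, ≥5, a score of 5 belongs to both the second and the third band, so Table 52 cannot be filled without a further rule.

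**The case against.** The strongest reply is that nothing is lost. An empty column removes no patient and changes no count in the other columns, the analysis is exploratory, and the bands come from a cited source. All of that stands, and it keeps the point minor. It does not make the low class meaningful in this population.

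A reader might go further in three ways that the documents do not support.

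- **That Table 50 is the only planned display of dose against bleeding risk.** It is not. Table 51 shows dabigatran dosing by HAS-BLED <3 and ≥3 at ages 75-79. Table 50 is the only one covering all four NOACs.
- **That the remaining bands are too coarse.** This is largely judgement. The ≥3 cut has a use in 7.2.17, and Tables 15 and 25 also give the score's mean, median, quartiles and range. What can be said is that Table 50 has no such summary and cannot separate score 1 from score 2.
- **That an erroneous 0 would pass unnoticed.** This is not known. Protocol 9.6 provides for eCRF checks on illogical or out-of-range data, but their specification was not available for this review. A 0 would also appear as the minimum in Tables 15 and 25.

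Finer bands also cost precision. The SAP asks for at least 50 patients in its listed subgroups (8.5). That rule does not name Table 50, but the even-spread figure for three bands (41.7) falls below it. The argument counts against making four bands compulsory. It has little force against splitting 1-2, because those two columns can be added back together.

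**Conclusion.** The point holds as a minor defect of definition. Score 0 is unattainable for anyone in the Full Analysis Set, so one of the three HAS-BLED classes is empty by construction and the planned dose description has two levels. This rests only on the SAP's age item and age criterion, and on age carrying some positive weight.

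No estimate is shown to be biased. The primary outcome, the percentage of patients by NOAC type and dose, does not use HAS-BLED. How often a 0 might be recorded cannot be judged from the documents. The possible carry-over into the dabigatran classification is a reason to look, not a demonstrated error.

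**What to change.** - In SAP 7.2.16 and 14.6 and in Tables 15, 25 and 50, replace the bands with 1, 2 and ≥3. This keeps the cut used in 7.2.17 and restores three usable levels. A further split at ≥4 is optional if counts allow. Label the bands by score, and note that 0 cannot occur because every patient meets the age item.
- Query any recorded HAS-BLED of 0 with the site before analysis. Planned data collection ended in April 2020 (protocol 6) and the SAP is dated 08072020, so this may have to be a data query rather than a live eCRF check. Where a 0 proves to come from omitting the age item, consider checking that site's other totals.
- Remove the overlap at 5 in the Table 52 grouping, and align it with the bands above or state why it differs.

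The cost is SAP wording, the shells of Tables 15, 25, 50 and 52, and one query. No new variable is needed. The only statistical price is smaller cells in Table 50, and summing the 1 and 2 columns recovers the present 1-2 class.
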